6. ANALYSIS INTERPRETATION

All analyses are descriptive.

CONFIDENTIAL207350 (EPI-HPV-070 VS CN PMS)
Statistical Analysis Plan

7. CONDUCT OF ANALYSES

7.1. Sequence of analyses

A final analysis of all data collected up to either 12 months following the third immunisation or 24 months following the first immunisation with *Cervarix* (whichever occurs first), will be conducted. This will include final analysis of safety. In case of regulatory submission before license renewal, interim report(s)/progress report(s) will be prepared. The analysis for the annual progress reports will be performed on the dataset that will be as cleaned as possible that includes cumulative number of subjects recorded in the clinical database until the date of data lock point.

The data to be analysed will be selected based on date of consent (demography), date of completion/withdrawal (disposition), dates of administration (study vaccine, concomitant vaccines/medications) or onset dates (AEFI, pregnancy outcomes) prior to or on the date of data lock point, as applicable.

Since the study started on May 31, 2018, the DLP (Data Lock Point) was set as May 31, 2019 for the ADR report 2019 and May 31, 2020 for the ADR report 2020. The dates of clinical database freeze will be adjusted accordingly following data cleaning and SAE (Serious Adverse Events) reconciliation, thus may encompass data beyond DLP as this is a living database.

After the DBF of final analysis, If there are any additional information collected during the infant follow up on potential congenital anomalies when the child is about 12 months old, the listing related to adverse events of infants will be updated post another DBF.

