# Investigator will check with the subjects, if they are pregnant or planning to get pregnant before administration of any dose of Cervarix

**CONFIDENTIAL**

207350 (EPI-HPV-070 VS CN PMS)  
Protocol Amendment 1 Final

^ is used to indicate that the procedure is performed as per routine and standard practice.

^Vaccination history: Record any vaccinations administered in the 12 months preceding visit 1.

AEFI: Adverse Event Following Immunisation.

\* The (FU) follow-up period will be extended until 1 year post-delivery to check for any neonatal birth defects/congenital anomalies.

Imm = immunisation

M: Month

\*\* Only applies to pregnancies where it is documented that *Cervarix* was administered within 60 days before pregnancy onset or anytime during pregnancy (pregnancies starting more than 60 days after the last immunisation with *Cervarix* will not be reported).

^^ In case of pregnancy follow-up, the study conclusion for the subject and the new-born child will be the collection of information on potential congenital anomalies when the child is about 12 months old.

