**9.2.5.2.9. Reporting of pregnancies (outcomes and congenital anomalies)**

The investigator will record any PO or congenital anomalies only in cases where it is documented that *Cervarix* was administered within 60 days before pregnancy onset or anytime during pregnancy. Pregnancies that occur 60 days following the last immunisation with *Cervarix* will not be reported. Pregnant women will be followed-up until end of pregnancy to determine the PO, which will be documented. Any congenital anomaly diagnosed during the first 12 months of the child's life will be recorded in the eCRF.

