2.2.2. Secondary endpoints

- Occurrence, intensity and causal relationship to vaccination of serious AEFI reported during the period starting at the first immunisation and ending either 12 months following the third immunisation or 24 months following the first immunisation with *Cervarix* (whichever occurs first), in all enrolled subjects.
- Occurrence, intensity and causal relationship of pIMDs detected during the period starting at the first immunisation and ending either 12 months following the third immunisation or 24 months following the first immunisation with *Cervarix* (whichever occurs first), in all enrolled subjects.

CONFIDENTIAL207350 (EPI-HPV-070 VS CN PMS)
Statistical Analysis Plan

- Occurrence of PO when *Cervarix* is administered inadvertently within 60 days before pregnancy onset or any time during pregnancy.
- Occurrence of any congenital anomalies when *Cervarix* is administered inadvertently within 60 days before pregnancy onset or any time during pregnancy.

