5.4.2. Analysis for Secondary endpoints

The analysis will be based on the ES.

The occurrence of serious AEFIs will be assessed throughout the entire follow-up period. Serious AEFIs will be further evaluated for their clinical relevance and relationship to vaccination.

The percentage of subjects with serious AEFI occurring within the 30-day (Day 1-30) follow-up period will be tabulated with exact 95% CI after any dose.

The occurrence of pIMD(s) will be collected and summarized through the entire follow-up period in all exposed subjects.

The PO and congenital anomalies will be summarized when *Cervarix* is administered within 60 days before pregnancy onset or any time during pregnancy. In addition, the PO will be summarized by the time of the vaccination, such as vaccination before the pregnancy, vaccination during the first trimester (LMP through week 13) of the pregnancy, vaccination during the second trimester (week 14 through week 27) of the pregnancy, vaccination during the third trimester (week 28 through term) of the pregnancy.

All secondary endpoints (serious AEFIs, pIMDs and POs) will be summarized by percentage of subjects reporting the endpoint with exact 95% CI.

CONFIDENTIAL207350 (EPI-HPV-070 VS CN PMS)
Statistical Analysis Plan**5.4.3. Additional considerations**

The percentage of subjects with at least one medically attended non-serious AEFI occurring within the 30-day (Day 1-30) follow-up period will be tabulated with exact 95% CI after any dose.

The percentage of subjects, who have used any medications, that was required to be reported as per protocol, during the whole study period will be tabulated. Medications will be coded using the GSKDRUG dictionary.

All primary and secondary endpoints (medically attended AEFIs, serious AEFIs, , casually related AEFIs , grade 3 AEFIs, pIMDs and POs) will be summarized by percentage of subjects and percentage of doses reporting the symptoms with exact 95% CI.

Incidence and nature of reported AEFIs following each dose and overall will be presented. The analysis will be done for any AEFI, medically attended AEFI within 30 days follow-up period and serious AEFI.

Adverse events will be coded using medical dictionary for regulatory activities - MedDRA classification of System Organ Class and Preferred term.

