7.2. Statistical considerations for interim analyses

Since there is no hypothesis testing, no adjustment of type I error is required. A final report will be prepared when the follow-up of all enrolled subjects has been completed.

CONFIDENTIAL

207350 (EPI-HPV-070 VS CN PMS)
Statistical Analysis Plan

The following table details the analyses (tables and figures) to be included in each analysis (interim and final analysis)

Description	Analysis ID	Disclosure Purpose	Dry run review needed (Y/N)	Study Headline Summary (SHS)	Reference for TFL
Analysis of all data	E1_01	Study report	Yes	Yes	All tables from TFL TOC
Analysis of data as of DLP = 31May2019	E1_02	Comprehensive report to be submitted to ADR	No	No	Additional analysis request Amendment dated 01-Oct-2019
Analysis of data as of DLP = 31May2020	E1_03	Comprehensive report to be submitted to ADR	No	No	Additional analysis request Amendment dated 01-Oct-2019

NA: Not applicable

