10.1.3.3. Distinction of adverse events in mother and infant cases

For the pregnant subjects with pregnancy outcome, in case if there are any adverse events collected for both mother and infants, adverse events of the infants will be prefixed with the term - 'INFANT' to distinguish between the AEs of mother and the infant. Analysis of primary and secondary endpoints (AEs of the subjects), data needs to be considered accordingly. (E.g., If the analysis is based on the AE of the subjects, then we need to exclude the AE's prefixed with the word 'Infant'.)

CONFIDENTIAL207350 (EPI-HPV-070 VS CN PMS)
Statistical Analysis Plan**10.1.4. Display of decimals****10.1.4.1. Percentages**

Percentages and their corresponding confidence limits will be displayed with:

- no decimals when there are fewer than 50 subjects in each tabulated group
- one decimal when there are at least 50 subjects in at least one tabulated group
 - o Exceptions will be made for percentages that are not 0% or 100% but appear as 0% or 100% due to rounding. For these specific cases the number of decimals will be increased until the displayed value is no longer 0% or 100%. Examples are given in the following table.

n/N	Displayed percentage
10/45	22%
1/45	2%
10/55	18.2%
1/55	1.8%
1/300	0.3%
1/3000	0.03%
1/30000	0.003%
299/300	99.7%
2999/3000	99.97%
29999/30000	99.997%

- o The display of additional decimals for values close to 0% or 100% will be applied only to point estimates and not confidence limits, which can be rounded and displayed as 0% or 100%.
- o Values of exactly 0% or 100% will be presented with no decimals regardless of the number of subjects per tabulated group.

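### SAP 7.1 updates only the infant listing if 12-month infant information arrives after the final freeze; the congenital-anomaly summary in SAP 5.4.2 is left out of that update

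*SAP*

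**What the plan says.** SAP 2.2.2 lists as a secondary endpoint "Occurrence of any congenital anomalies when" the vaccine was given inadvertently in the 60 days before pregnancy onset or during pregnancy. Protocol 9.2.5.2.9 sets the ascertainment window: "Any congenital anomaly diagnosed during the first 12 months of the" child's life is recorded in the eCRF. A footnote to Table 2 (Protocol 9.2.4) makes study conclusion for pregnancy cases the "collection of information on potential congenital anomalies when the child is about 12 months old".

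For the analysis, SAP 5.4.2 states: "The PO and congenital anomalies will be summarized when" exposure falls in that period. SAP 7.1 opens with "A final analysis of all data collected up to either 12 months following the third immunisation or 24 months following the first immunisation", whichever comes first. It closes with a contingency: should more infant information at about 12 months of age be collected after the final-analysis freeze, "the listing related to adverse events of infants will be updated post another DBF".

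The table in SAP 7.2 has three analyses: one of all data (E1_01) and one for each data lock point, 31 May 2019 and 31 May 2020 (E1_02, E1_03). SAP 7.2 also says "A final report will be prepared when the follow-up of all enrolled subjects has been completed". SAP section 8, on changes from planned analyses, does not mention infant data.

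**The concern.** The endpoint has a 12-month window per child, but the plan finalises its summary at a freeze that some children may reach before 12 months. For those children the later information goes into a listing and the summary stays as it was. Two outputs from the same study could then differ on the number of anomalies, with no statement of which is final.

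The subject-level adverse-event tables cannot close the gap. A congenital anomaly in the offspring counts as a serious AEFI under Protocol 9.3.1.3, but SAP 10.1.3.3 marks infant events with a prefix and says: "If the analysis is based on the AE of the subjects, then we need to exclude" them.

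The matter deserves attention because, according to Protocol 7.1, the approval letter names neonatal birth defects among the information to be collected.

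**Working it through.** The plan states no figure to reproduce. The check has a textual part and a timing part.

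**Text.** Nothing in SAP 5.4.2, 5.4.3, 7.1, 7.2 or 8 commits to re-running the congenital-anomaly summary after the final freeze. The only output attached to the second freeze is the listing in the last paragraph of 7.1.

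**Can an infant be under 12 months at the final freeze?**

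Inputs from the documents:
- latest eligible onset: 60 days after the last dose (SAP section 3);
- infant window: 12 months;
- Call 3: 12 months after dose 3, or 24 months after dose 1 if earlier;
- tentative milestones (Protocol section 6): data collection ends Q1 2021, final report Q4 2021;
- study start: 31 May 2018 (SAP 7.1).

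Assumptions: gestation g of 266 to 280 days from onset (pregnancy onset is not defined); a month of 30.4375 days; the freeze dates used below.

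1. Gap between Call 3 and the 12-month infant check, for dose 3 given by month 12 and onset 60 days after it: (60 + g) / 30.4375 = 326 / 30.4375 = 10.7 months, to 340 / 30.4375 = 11.2 months. With onset on the day of dose 3 and g = 280: 280 / 30.4375 = 9.2 months. For exposures around dose 3, infant follow-up that continues after the mother's Call 3 is a normal result of the design.

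2. Late-end scenario. Suppose the last dose 3 is on 31 March 2020, that is, 12 months before the end of Q1 2021. Window end = dose 3 + offset + g + 365 days.
 - Offset 60: + 691 or + 705 days, giving 20 February to 6 March 2022.
 - Offset 0: + 631 or + 645 days, giving 22 December 2021 to 5 January 2022.

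 With offset 60 the birth falls between 20 February and 6 March 2021. The child is 0.8 to 1.3 months old at an assumed freeze on 31 March 2021, and 9.9 to 10.3 months old at an assumed freeze on 31 December 2021.

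3. Who is incomplete? With onset 60 days after dose 3, an infant is incomplete only if dose 3 came later than the freeze date minus 691 to 705 days.
 - Freeze 31 March 2021: dose 3 after 26 April to 10 May 2019.
 - Freeze 31 December 2021: dose 3 after 26 January to 9 February 2020.

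4. Early enrolment. For a subject enrolled on 31 May 2018, dose 3 at month 5 (30 October 2018) gives a latest window end of 20 September to 4 October 2020. Dose 3 at month 6 (30 November 2018) gives 21 October to 4 November 2020. Both are complete before either assumed freeze.

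**What one late case would do.** With an assumed 20 infants, and if a proportion with an exact interval is reported, one late anomaly moves the result from 0/20 (95% CI 0 to 16.8%) to 1/20 (5.0%, 0.1 to 24.9%). The upper limit moves from 30.8% to 44.5% for an assumed 10 infants, and from 7.1% to 10.6% for an assumed 50.

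**The case against.** The strongest reply is that little is at risk. SAP section 6 makes every analysis descriptive, and Protocol 9.12 already says that few pregnancy exposures are expected. SAP 5.4.3 plans listings of infants with and without anomalies, so with few cases a reader could recount from the updated listing. The form of the summary is also unsettled: the sentence on percentages with exact intervals covers all secondary endpoints, but its bracket names serious AEFIs, pIMDs and pregnancy outcomes, not congenital anomalies. The table layouts are in a separate document that is not available here and may show infant follow-up status. All of this stands, and it limits the weight of the point. It does not supply the missing commitment to refresh the summary.

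Three stronger inferences are tempting, and the documents do not support them.

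- A reader might infer that the SAP expects late infant data. The last paragraph of 7.1 is conditional; it provides for the case without predicting it.
- A reader might take the 12/24-month limit in 7.1 as cutting off infant data too, so that no live birth exposed at dose 3 could be complete. That reading is strained. SAP section 3 extends follow-up of exposed pregnancies beyond 24 months, E1_01 covers all data, and 7.1 treats infant information after the freeze as additional. The natural reading is that infant data count up to the freeze, so only infants under 12 months on that date are concerned.
- A reader might see 7.1 and 7.2 as contradicting each other. One concerns a database freeze, the other the timing of the report. If the report follows the second freeze, both hold, and the Table 2 footnote on study conclusion fits that sequence.

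**Conclusion.** The point holds as an omission with a practical consequence. Applied as written, SAP 7.1 would leave the summary of a secondary endpoint as it stood at the final freeze while the infant listing moved on. Confidence in the textual omission is high.

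The size is unknown. The dates above depend on assumed freeze dates, an assumed gestation and tentative milestones. They also take the last Call 3 to fall at the very end of Q1 2021. The checklist in Protocol Annex 10 defines the end of data collection as the date when the analytical dataset is complete, so the last Call 3 could be earlier and the affected group smaller. If the final freeze came after the last 12-month infant check, no infant would be affected.

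It would be wrong to conclude that late anomalies are lost, since they reach the listing, or that the primary endpoint is touched. This is a worthwhile and inexpensive improvement to one descriptive result.

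**What to change.** Amend SAP 7.1 so that, at the second freeze it already provides for, the 5.4.2 congenital-anomaly summary is re-run together with the infant listing and reported as the final result for that endpoint. Give this run its own line in the SAP 7.2 table. In the first analysis, show how many live-born infants have completed 12 months of follow-up, so that the summary can be read for what it is.

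As clarification only, state in 7.1 that infant data from exposed pregnancies are included up to the freeze and are not cut at the mother's 12/24-month limit, and say whether the final report follows the second freeze.

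The cost is a few lines of SAP text and one repeat of a descriptive table. Data collection does not change. The downside is that one descriptive endpoint is finalised later than the rest.

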7.2. Statistical considerations for interim analyses

Since there is no hypothesis testing, no adjustment of type I error is required. A final report will be prepared when the follow-up of all enrolled subjects has been completed.

CONFIDENTIAL

207350 (EPI-HPV-070 VS CN PMS)
Statistical Analysis Plan

The following table details the analyses (tables and figures) to be included in each analysis (interim and final analysis)

Description	Analysis ID	Disclosure Purpose	Dry run review needed (Y/N)	Study Headline Summary (SHS)	Reference for TFL
Analysis of all data	E1_01	Study report	Yes	Yes	All tables from TFL TOC
Analysis of data as of DLP = 31May2019	E1_02	Comprehensive report to be submitted to ADR	No	No	Additional analysis request Amendment dated 01-Oct-2019
Analysis of data as of DLP = 31May2020	E1_03	Comprehensive report to be submitted to ADR	No	No	Additional analysis request Amendment dated 01-Oct-2019

NA: Not applicable

8. CHANGES FROM PLANNED ANALYSES

All analyses related to primary and secondary endpoints except on study attrition will be done on the exposed set instead of all enrolled subjects as planned in the protocol.

9. NON-STANDARD DATA DERIVATION RULES AND STATISTICAL METHODS

Not applicable.

CONFIDENTIAL207350 (EPI-HPV-070 VS CN PMS)
Statistical Analysis Plan

10. ANNEXES

10.1. Business rules for standard data derivations and statistical methods

This section contains GSK Vaccines' standard rules for data display and derivation for clinical and epidemiological studies. These rules will be applied along with those detailed in section 9 (additional study-specific rules).

10.1.1. Attributing events to vaccine doses

The dose relative to an event is the most recent study dose given to a subject prior to the start of a given event. For example, if the start date of an adverse event is between Dose 1 and Dose 2, the relative dose will be Dose 1.

If an event starts on the same day as a study dose, the relative dose will be derived from the additional information provided in the CRF using the contents of the flag indicating if the event occurred before or after vaccination. If 'after vaccination' is selected, the relative dose for the event will be the one administered on the start day of the event. If 'before vaccination' is selected, the relative dose for the event will be the dose prior to this one.

10.1.2. Handling of missing data

10.1.2.1. Dates

When partially completed dates (i.e. with missing day or month) are used in calculations, the following standard rules will be applied:

- A missing day will be replaced by 15
- A missing day and month will be replaced by June 30th.

The following exceptions apply:

- Adverse event start dates with missing day:
 - o If the event starts in the same month as at least one of the study doses, the contents of AE.AESTRTPT (the flag indicating if the event occurred before or after vaccination) will be used to complete the date. If 'after vaccination' is selected, the imputed start date will match the first (or only) study dose given during that month. If 'before vaccination' is selected, the imputed date will be one day before the first (or only) study dose given during that month.
- Adverse event start dates with missing day and month:
 - o If the event starts in the same year as at least one of the study doses, the contents of AE.AESTRTPT (the flag indicating if the event occurred before or after vaccination) will be used to complete the date. If 'after vaccination' is selected, the imputed start date will match the first (or

CONFIDENTIAL

207350 (EPI-HPV-070 VS CN PMS)
Statistical Analysis Plan

only) study dose given during that year. If 'before vaccination' is selected, the imputed date will be one day before the first (or only) study dose given during that year.

All other cases of incomplete AE or concomitant medication/vaccination start date will follow the standard rules above.

10.1.2.2. Laboratory data

Not applicable.

10.1.2.3. Daily recording of solicited adverse events

Not applicable.

10.1.2.4. Unsolicited adverse events

Unsolicited adverse event summaries are including serious adverse events unless specified otherwise.

Missing severity, relationship with study vaccine, and outcome of unsolicited adverse events will not be replaced and will appear as 'UNKNOWN' in all statistical output.

10.1.3. Data derivation

10.1.3.1. Age at vaccination in years

When age at vaccination is to be displayed in years, it will be calculated as the number of complete calendar years between the date of birth and the date of vaccination. For example:

DOB = 10SEP1983, Date of vaccination = 09SEP2018 -> Age = 34 years

DOB = 10SEP1983, Date of vaccination = 10SEP2018 -> Age = 35 years

10.1.3.2. Duration of events

The duration of an event with a start and end date will be the number of days between the start and end dates plus one day, i.e. an event that starts on 03MAR2018 and ends on 12MAR2018 has a duration of 10 days.

10.1.3.3. Distinction of adverse events in mother and infant cases

For the pregnant subjects with pregnancy outcome, in case if there are any adverse events collected for both mother and infants, adverse events of the infants will be prefixed with the term - 'INFANT' to distinguish between the AEs of mother and the infant. Analysis of primary and secondary endpoints (AEs of the subjects), data needs to be considered accordingly. (E.g., If the analysis is based on the AE of the subjects, then we need to exclude the AE's prefixed with the word 'Infant'.)

CONFIDENTIAL207350 (EPI-HPV-070 VS CN PMS)
Statistical Analysis Plan**10.1.4. Display of decimals****10.1.4.1. Percentages**

Percentages and their corresponding confidence limits will be displayed with:

- no decimals when there are fewer than 50 subjects in each tabulated group
- one decimal when there are at least 50 subjects in at least one tabulated group
 - o Exceptions will be made for percentages that are not 0% or 100% but appear as 0% or 100% due to rounding. For these specific cases the number of decimals will be increased until the displayed value is no longer 0% or 100%. Examples are given in the following table.

n/N	Displayed percentage
10/45	22%
1/45	2%
10/55	18.2%
1/55	1.8%
1/300	0.3%
1/3000	0.03%
1/30000	0.003%
299/300	99.7%
2999/3000	99.97%
29999/30000	99.997%

- o The display of additional decimals for values close to 0% or 100% will be applied only to point estimates and not confidence limits, which can be rounded and displayed as 0% or 100%.
- o Values of exactly 0% or 100% will be presented with no decimals regardless of the number of subjects per tabulated group.

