### 9.3.1.3. Serious AEFI

A serious AEFI is any untoward medical occurrence that:

- Results in death.
- Is life-threatening
  - The term 'life-threatening' in the definition of 'serious' refers to an event in which the subject was at risk of death at the time of the event. It does not refer to an event, which hypothetically might have caused death, had it been more severe.
- Requires hospitalisation or prolongation of existing hospitalisation.
  - In general, hospitalisation signifies that the subject has been admitted at the hospital or emergency ward for observation and/or treatment that would not have been appropriate in the physician's office or out-patient setting. Complications that occur during hospitalisation are also considered AEFIs. If a complication prolongs hospitalisation or fulfils any other serious criteria, the event will also be considered serious. When in doubt as to whether 'hospitalisation' occurred or was necessary, the AEFI should be considered serious. Hospitalisation for elective treatment of a pre-existing condition (known/diagnosed prior to informed consent signature) that did not worsen from baseline is NOT considered an AEFI.
- Results in disability/incapacity, or
  - NB: The term disability means a substantial disruption of a person's ability to conduct normal life functions. This definition is not intended to include experiences of relatively minor medical significance such as uncomplicated headache, nausea, vomiting, diarrhoea, influenza, and accidental trauma (e.g. sprained ankle) which may interfere or prevent everyday life functions but do not constitute a substantial disruption.
- Is a congenital anomaly/birth defect in the offspring of a subject.

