### 11.1.2.2. Assessment of causality

In case of any medically attended AEFI occurring within the 30 days following each immunisation with *Cervarix*, serious AEFI, pIMDs or PO (elective abortion for medical reasons or spontaneous abortion or congenital anomaly), the investigator should assess the causality. The investigator will use clinical judgement to determine the relationship. Alternative causes, such as natural history of the underlying diseases, other concomitant therapy and other risk factors will be considered and investigated. The investigator will

also consult the Product Information (Summary of Product Characteristics) to determine his/her assessment.

There may be situations when a serious AEFI has occurred and the investigator has minimal information to include in the initial report to GSK Biologicals. However, it is very important that the investigator always makes an assessment of causality for every event prior to submission of the serious AEFI to GSK Biologicals. The investigator may change his/ her opinion of causality in light of follow-up information and update the serious AEFI information accordingly. The causality assessment is one of the criteria used when determining regulatory reporting requirements.

Causality should be assessed by the investigator using the following question:

Is there a reasonable possibility that the AEFI/serious AEFI/pIMD may have been caused by the vaccine?

YES : There is a reasonable possibility that the vaccine contributed to the AEFI/pIMD.

NO : There is no reasonable possibility that the vaccine contributed to the AEFI/pIMD. There are other, more likely causes and administration of the vaccine is not suspected to have contributed to the AEFI/pIMD.

Possible contributing factors include:

- Medical history
- Other medication
- Protocol required procedure
- Other procedure not required by the protocol
- Erroneous administration
- Other cause (specify).

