**Prospective study:**

A study in which the subjects/cases are identified and then followed forward in time in order to address one or more study objectives.

Research protocol:	A document that describes the objective(s), design, methodology, statistical considerations, and organization of a trial. The protocol usually also gives the background and rationale for the trial, but these could be provided in other protocol referenced documents.
Self-contained study:	Study with objectives not linked to the data of another study.
Serious adverse event:	Any untoward medical occurrence in a subject that: results in death, is life-threatening, requires hospitalization or prolongation of existing hospitalization, results in disability/incapacity, or is a congenital anomaly/birth defect in the offspring of a study subject.
Study population:	Sample of population of interest.
Subject:	Term used throughout the protocol to denote an individual who has been contacted in order to participate or participates in the clinical/ epidemiological study, or a person about whom some medical information has been recorded in a database.
Surveillance:	The ongoing systematic collection, collation, analysis, and interpretation of descriptive epidemiological health data on a specific disease. Surveillance can monitor incidence and/or prevalence, and/or inform about when and where health problems are occurring and who is affected.

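### SAP 10.1.3.3 excludes infant events from analyses of the subjects' AEs with no stated exception for congenital anomalies, which the protocol counts as a serious AEFI of the mother

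*SAP*

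**What the plan says.** **The SAP rule.** SAP 10.1.3.3 applies "in case if there are any adverse events collected for both mother and infants"; infant events then carry the prefix 'INFANT'. It continues "Analysis of primary and secondary endpoints (AEs of the subjects), data needs to be considered accordingly", and gives as its example "E.g., If the analysis is based on the AE of the subjects, then we need to exclude the AE's prefixed with the word 'Infant". No type of infant event is exempted.

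**The protocol definition.** Protocol 9.3.1.3 lists among the criteria for a serious AEFI: "Is a congenital anomaly/birth defect in the offspring of a subject". The glossary (Annex 2) defines a serious adverse event as an occurrence in a subject, and one criterion is that it "is a congenital anomaly/birth defect in the offspring of a study subject". Protocol 11.1.2.2 requires a causality judgement: for a "serious AEFI, pIMDs or PO (elective abortion for medical reasons or spontaneous abortion or congenital anomaly), the investigator should assess the causality".

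**The analyses affected.** SAP 2.2.2 sets the serious AEFI endpoint as "Occurrence, intensity and causal relationship to vaccination of serious AEFI reported during the period starting at the first immunisation", ending 12 months after dose 3 or 24 months after dose 1, whichever is first. SAP 5.4.2 gives the percentage of subjects with an exact 95% CI. SAP 5.4.3 adds a summary of serious AEFIs and a matching one for those judged related.

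**What else covers anomalies.** They have their own secondary endpoint (SAP 2.2.2), a summary (5.4.2), an infant listing (5.4.3) and a late update of the infant AE listing (7.1). Section 8 declares one change from the protocol, the use of the Exposed Set. The table shells are in a separate TFL document (10.2).

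**The concern.** Under the protocol a congenital anomaly is the one infant event that is also, by definition, a serious event of the mother. The SAP's exclusion is written for infant events in general. A programmer who applies it as written could remove that event from an endpoint to which the protocol assigns it, and nothing in SAP 5.4.2, 5.4.3, 8 or 9 puts it back.

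What is at stake is the agreement between tables. Because the investigator judges causality for anomalies, one could be classed as related. The related-serious summary might then show no events while the infant listing shows a related anomaly. Protocol 7.1 records that the approval letter asked specifically for the effect on pregnancy outcomes, including birth defects, so readers are likely to compare those outputs.

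**Working it through.** **1. Readings of the rule**

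| Reading | What is prefixed | Effect on the mother's serious AEFI count |
|---|---|---|
| (a) Broad | Every infant event | A qualifying anomaly is dropped |
| (b) Literal | Infant events only where the mother also has an AE | Dropped if she has another AE, counted if she has none |
| (c) Benign | Infant events other than qualifying anomalies | Counted as her own event |

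Reading (c) matches the protocol, but the SAP does not state it. Under (b), the same anomaly is handled differently according to whether the mother also had an AE. If that AE is itself serious, she is already counted once.

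**2. Size of the effect on the tables**

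Inputs: n = 3000 (minimum Exposed Set, Protocol 9.5.1); 0.5% planning value, 15 subjects (Table 5); Clopper-Pearson limits (SAP 10.1.5.1); display rule "one decimal when there are at least 50 subjects in at least one tabulated group" (SAP 10.1.4.1), with extra decimals only for point estimates that would otherwise round to 0% or 100%. The method reproduces the protocol's Table 5 figure for 15/3000: 0.28% to 0.82%.

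| Count / 3000 | Unrounded, % (95% CI) | As printed |
|---|---|---|
| 15 | 0.500 (0.280, 0.823) | 0.5 (0.3-0.8) |
| 14 | 0.467 (0.255, 0.782) | 0.5 (0.3-0.8) |
| 13 | 0.433 (0.231, 0.740) | 0.4 (0.2-0.7) |
| 1 | 0.033 (0.0008, 0.186) | 0.03, upper limit 0.2 |
| 0 | 0 (0, 0.123) | 0, upper limit 0.1 |

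One omission changes only the raw count in the overall row; two change the printed percentage. In the related-serious row a single omission is the difference between one event and none.

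**3. How likely a qualifying case is**

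The documents give no expected number, so this is an illustration scaled from the reference trial HPV-039 (Protocol 7): 6051 women, 1683 pregnancies, 72 months (Protocol 9.5.1), five live-born infants with anomalies.

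- Pregnancy rate, assuming full follow-up: 1683 / (6051 x 6) = 0.0464 per woman-year.
- Exposed time per woman (onset within 60 days after a dose): about 150 days on a 0, 1, 6 month schedule, where the first two windows overlap, to 180 days without overlap.
- Exposed pregnancies: 3000 x (150 to 180)/365.25 x 0.0464 = 57 to 69. Women already pregnant at a dose are not added.
- Live-born anomalies: (57 to 69) x 5/1683 = mean 0.170 to 0.204.
- Time window: onset 0 to 60 days after dose 3 and a 280-day term (assumed) leave 365 - 340 = 25 to 365 - 280 = 85 days before the serious AEFI period ends. Dose 3 accounts for 60/180 to 60/150 = 33-40% of exposed time. If none of those anomalies is reported in time, the mean is 0.170 x 90/150 = 0.102 to 0.204 x 120/180 = 0.136. If all are, it stays 0.170 to 0.204.
- Broad reading, P(at least one) = 1 - exp(-mean): 1 - exp(-0.102) = 0.10 to 1 - exp(-0.204) = 0.18. With the pregnancy rate halved (means 0.051 to 0.102): 0.05 to 0.10. Overall about 5-18%.
- Literal reading: the mother must also have an AE. Taking the protocol's 0.20-1.0% planning range for medically attended AEFIs (an assumption; it may be higher in pregnancy), 0.102 x 0.002 = 0.0002 to 0.204 x 0.010 = 0.0020, or about 0.02-0.2%.

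The anomaly rate pools both trial groups. All five live-born cases were in the HPV group, and the split of pregnancies by group is not given. If half were in that group (an assumption), the top mean would double to 0.41 and P to 1 - exp(-0.41) = 0.33; zero would still be the likeliest count.

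**The case against.** The best defence is reading (c). The protocol places the anomaly with the subject, so it is already one of her own AEs, and the prefix serves only to separate other infant events. The SAP wording is loose enough to allow this: the instruction is an example, in a section of standard display and derivation rules. On this reading nothing is excluded and Section 8 has nothing to declare. That is a fair reading and would be the right outcome. It does not close the point, because the SAP never says so and the plain instruction points the other way.

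The second defence is that anomalies are already reported under their own endpoint, and that counting them again in the serious AEFI row is partly a matter of presentation. This stands as a limit on the harm. A reader might infer that the rule hides birth defects from the report; the separate summary, the infant listing and its late update rule that out. But separate reporting does not make the serious AEFI tables follow the protocol's definition.

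Third, the likelihood rests on women who enrolled at 18-25, while this cohort is aged 9-45 and is asked about pregnancy and pregnancy plans before each dose (Protocol 9.2.5.2.4). This also stands, and it is why a halved pregnancy rate is shown.

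Finally, the TFL document may settle the matter. It was not available, so it can neither be relied on nor ruled out. Excluding ordinary infant illnesses from the mothers' tables is sensible and is not in dispute.

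**Conclusion.** The conflict is real and minor. On the plain reading of SAP 10.1.3.3, the serious and related-serious AEFI counts can depart from the protocol's definition, and the SAP neither makes an exception nor declares the departure.

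The documents do not support the stronger statement that a qualifying anomaly will be dropped, since one of the three readings keeps it. Nor do they support a claim of material bias in the serious AEFI percentage: one omitted case leaves the printed figure at 0.5% (0.3-0.8).

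The visible one-case effect is in the related-serious row, 0% instead of 0.03%. The chances of about 5-18% (broad reading) and 0.02-0.2% (literal reading) are only upper bounds for that change, because it also needs a judgement of 'related', whose probability the documents do not give. All these likelihoods rest on the pooled HPV-039 rates and the timing assumptions shown. If no qualifying case occurs, which is the likeliest outcome, the effect is nil.

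Confidence is medium, because the TFL document was not seen.

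**What to change.** Reword SAP 10.1.3.3 so that INFANT-prefixed events are excluded from subject-level tables except congenital anomalies that meet the protocol's serious AEFI definition and are reported within the serious AEFI period, whether or not the mother has another AE. Count the mother once in the serious AEFI table, and in the related-serious table if the anomaly is judged related.

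State that the report date decides the window. The endpoint in SAP 2.2.2 speaks of events reported, whereas the objective in 2.1.2 speaks of events occurring. Anomalies reported later would then appear only in the separate anomaly outputs, which mainly affects exposures around dose 3.

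Alternatively, keep the exclusion, declare it in SAP Section 8, and footnote both tables with the count including anomalies.

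The cost is a short text change, one derivation flag and one row or footnote, plus some overlap with the separate anomaly summary. No data collection changes.
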